#### 12 SAFETY REPORTING

#### 12.1 Terms and Definitions

Collectively, the terms and definitions below are referred to as 'safety events'.

#### **Adverse Event (AE)**

Any untoward medical occurrence, unintended disease or injury or any untoward clinical signs (including an abnormal laboratory finding) in subjects, users or other persons whether or not related to a medicinal product or medical device.

#### **Adverse Event of Special Interest (AESI)**

An AE thought to be potentially associated with the medical product or medical device under study.

#### Related Adverse Event (Related AE)

An AE with a relatedness assessment of either "possible", "probable" or "causal relationship".

#### **Adverse Device Effect (ADE)**

An AE which is a result of:

- insufficiencies or inadequacies in the instructions for use, the deployment, the implantation, the installation, the operation, or any malfunction of the investigational medical device, or
- a use error or intentional abnormal use of the device.

#### **Unanticipated Adverse Device Effect (UADE)**

An ADE which by its nature, incidence, severity or outcome has not been identified in the current version of the risk analysis report / "Instructions for Use" / protocol (i.e. considered "unexpected").

#### **Serious Adverse Event (SAE)**

An AE which meets the definition of 'serious'.

#### **Related Serious Adverse Event (Related SAE)**

A Related AE which meets the definition of 'serious'.

#### **Serious Adverse Device Effect (SADE)**

An ADE which meets the definition of 'serious'.

#### **Unanticipated Serious Adverse Device Effect (USADE)**

An ADE which meets the definition of 'serious'.

#### **Device Deficiency**

An inadequacy of an investigational medical device related to its identity, quality, durability, reliability, safety or performance, such as malfunction, use error or inadequacy in the information supplied by the manufacturer.

#### **Adverse Incident (AI)**

An event that causes, or has the potential to cause unexpected or unwanted effects involving the safety of device users (including patients) or other persons.

**IRAS Ref: 271885** Page 53 of 89

## 12.2 Responsibilities – Investigator

The Investigator is responsible for reporting safety events to LCTC in accordance with section 12.3.

## 12.3 Reporting requirements

Not all of the safety events listed in section 12.1 are reportable to LCTC

The safety profile of cemented and uncemented hip implants, and bone cements that are CE marked are very well known. It is therefore highly unlikely that this trial will reveal any new safety information relating to total hip arthroplasty. The recording of only Adverse Events of Special Interest, and Serious Adverse Events that are related to the device or procedure will not affect the safety of participants or the aims of the trial.

[figure not shown]
#### The following are reportable to LCTC:

- Any Adverse Event of Special Interest (AESI) with a severity grading of 3 or above according to the Clavien Dindo classification system^24 (see table D).
- Any Adverse Device Event that meets the definition of serious (see section 12.5) and is assessed as being related a device (i.e. an implant or bone cement).

No other safety events are required to be reported to LCTC. All safety events (regardless of the requirement to report to LCTC) are to also be recorded and reported as per local policy.

**IRAS Ref: 271885** Page 54 of 89

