## 7.8 Schedule of trial procedures

Table B below describes Workstream 1 procedures and their time-points.

Table B: Trial procedures

able B. That procedures						
	TIMEPOINT					
PROCEDURE	Screening	Baseline	Randomisation	Day of surgery	Routine 6 weeks Post-op (-3 weeks / +6 weeks)	3-6 months Post-op (-2 month / +2 months^)
Identify eligible patient from records	Х				•	
Approach patient and discuss trial	Х					
Obtain Consent	Х					
Randomise patient			Х			
Demographics	Х					
PROMS – Oxford Hip Score		Х			Х	Х
PROMS – EQ-5D-5L TM		Х			Χ	X
PROMS – Self-Administered Patient Satisfaction Scale					X	X
PROMS – Forgotten Joint Score		Х			Х	Х
PROMS – Work Productivity and Activity Impairment–Specific Health Problem		Х			Х	Х
Healthcare Resource Use Survey		Х				Х
Data collection on routine surgery				Х		
Report Serious Adverse Events or Incidents				X	X	Х

^Yet no later than October 2021

**IRAS Ref: 271885** Page 43 of 89

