## 12.4 Assessment of Severity

Important Note: A distinction is drawn between **severe** and **serious**. Severity is a measure of intensity, whereas seriousness is defined using the criteria in Section 12.5. However, any AE's with a severity grading of 4 or 5, according to the Clavien Dindo classification system^24 (i.e. life-threatening or fatal), also meet the criteria of serious.

Table D: Clavien Dindo classification system^24.

Grade	Definition
1	
 
Any deviation from the normal postoperative course without the need for pharmacological treatment or surgical, endoscopic and radiological interventions.
 
Allowed therapeutic regimens are: drugs as antiemetics, antipyretics, analgetics, diuretics and electrolytes and physiotherapy.
 
This grade also includes wound infections opened at the bedside.
 

2	
 
Requiring pharmacological treatment with drugs other than such allowed for grade 1 complications.
 
Blood transfusions and total parental nutrition are also included.
 

3a	Requiring surgical, endoscopic or radiological intervention – not under general anaesthesia.
3b	Requiring surgical, endoscopic or radiological intervention – under general anaesthesia.
4a	
 
Life-threatening complication (including CNS complications*) requiring intermediate care or intensive care management – single- organ dysfunction (including dialysis).
 

4b	
 
Life-threatening complication (including CNS complications*) requiring intermediate care or intensive care management – multi- organ dysfunction.
 

5	Death of a patient.
*brain ha	aemorrhage, ischemic stroke, subarachnoidal bleeding, but excluding

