#### 12.5 Assessment of Seriousness

**Important Note:** The assessment of seriousness of safety events should be performed by an appropriately delegated, medically qualified member of the site research team.

An AE is termed "serious" if it:

transient ischemic attacks.

- Led to a death, injury or permanent impairment to a body structure or a body function;
- Led to a serious deterioration in health of the subject, that either resulted in:
  - o a life-threatening illness or injury, or

**IRAS Ref: 271885** Page 57 of 89

- o a permanent impairment of a body structure or a body function, or
- in-patient hospitalisation or prolongation of existing hospitalisation (N.B. Planned hospitalisation for pre-existing condition, or a procedure required by the Clinical Investigation Plan, without a serious deterioration in health, is not considered a serious adverse event), or
- Medical or surgical intervention to prevent life threatening illness;
- Led to foetal distress, foetal death or a congenital abnormality or birth defect.

Note: the reporting of pregnancy as an SAE is not required.

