## 12.10Responsibilities - LCTC

The LCTC is undertaking safety reporting duties delegated by the trial sponsor.

It is the responsibility of LCTC to report Unanticipated Serious Adverse Device Effects to REC and Sponsor, and to MHRA. Reporting to MHRA will be via the Yellow Card Scheme.

Observations of the following Safety Events will be reported to the sponsor and REC in an expedited fashion:

- Any significant difference in quantity of SADEs by implant type that are judged to be clinically important.
- Any recommendations of oversight committees, where relevant for the safety of the subjects.

Staff at the LCTC will liaise with the Chief Investigator or designated Clinical Coordinator who will evaluate the expectedness of all SADE reports received.

The LCTC will send an annual safety report containing a list of all Serious Safety Events to REC.

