## 13.4 Study Discontinuation

The trial may be closed prematurely by the Trial Steering Committee. If termination occurs the Research Ethics Committee will be informed. Reasons for termination may include:

- The incidence or severity of SAEs/morbidity in this trial indicates a potential health hazard caused by the study treatment.
- It appears that participant enrolment is unsatisfactory with respect to quality and/or quantity or if data recording is severely inaccurate and/or incomplete.
- External evidence demanding trial termination.

**IRAS Ref: 271885** Page 65 of 89

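### Serious AESIs below Clavien Dindo grade 3 that are not linked to stem, socket or cement have no required route to LCTC, although other sections of the protocol assume they are reported

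*Protocol*

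**What the plan says.** The operative rule is the list in section 12.3. For reporting to LCTC it names two classes:

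- "Any Adverse Event of Special Interest (AESI) with a severity grading of 3 or above according to the Clavien Dindo classification system";
- "Any Adverse Device Event that meets the definition of serious (see section 12.5) and is assessed as being related a device", explained there as an implant or bone cement.

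It closes with "No other safety events are required to be reported to LCTC". Section 12.8.1 puts the same grade 3 limit on the Adverse Events CRF. Section 12.8.2 requires every SADE to be sent within 5 calendar days.

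Other places describe a different scope:

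- **Section 12.3, rationale paragraph:** defends recording AESIs, with no grade limit, and serious events related to the device or the procedure.
- **Section 12.6:** calls a serious event related to a device or the procedure a SADE and requires expedited reporting of it, then allows relatedness to be assigned only to stem, socket and bone cement.
- **Section 7.8, Table B:** has a row "Report Serious Adverse Events or Incidents", marked for day of surgery, 6 weeks and 3-6 months.
- **Section 7.5:** collects AESI data at 6 weeks without a grade limit.
- **Section 12.10:** "The LCTC will send an annual safety report containing a list of all Serious Safety Events to REC".
- **Section 13.4:** gives as one possible reason for closure "The incidence or severity of SAEs/morbidity in this trial indicates a potential health hazard caused by the study treatment".
- **Section 18.3:** dispenses with an ISDMC and gives the TSC independent oversight of safety and complications.

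**The concern.** Section 12.4 itself says that severity and seriousness are different things, and it makes only grades 4 and 5 automatically serious. The AESI rule nevertheless turns on severity alone, on a scale that follows the treatment given rather than the consequence for the patient. Some serious AESIs therefore fall below the reporting line.

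Three things are at stake. LCTC has committed itself to a list for the ethics committee that its own incoming data may not support. Sites have conflicting instructions about serious events related to the operation but not to a component. And the TSC, the only independent body overseeing safety in this trial, would work from an incomplete count of serious events that the protocol itself names as of special interest. Intra-operative and post-operative safety is also a stated secondary objective (section 2.3).

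**Working it through.** No arithmetic applies; the protocol states no figure on this point. The check sets the definitions against the reporting rules.

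**Step 1: can an AESI be serious at grade 1 or 2?** Table D defines grade 2 as "Requiring pharmacological treatment with drugs other than such allowed for grade 1 complications", and grade 1 as needing no such drugs and no surgical, endoscopic or radiological intervention. Section 12.5 makes an event serious through permanent impairment, or through a serious deterioration in health that results in, among other things, "in-patient hospitalisation or prolongation of existing hospitalisation". Two Table C examples follow:

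- Permanent nerve injury with no intervention: grade 1, and serious through permanent impairment.
- Pulmonary embolism or pneumonia treated with drugs, where a serious deterioration prolongs the stay or leads to readmission: grade 2, and serious.

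So the category exists. Section 12.7.1 implies the same: for the patient notes it lists serious adverse events separately from AESIs of grade 3 or above.

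**Step 2: which AESIs must reach LCTC?**

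| AESI | Reporting list in 12.3, and 12.8.1 | Section 12.6 | Result |
|---|---|---|---|
| Grade 3 or above | Reportable | Not needed | Reaches LCTC |
| Serious, grade 1-2, at least possibly related to stem, socket or cement | Reportable by the second class | SADE, expedited | Reaches LCTC |
| Serious, grade 1-2, related to the procedure only | Not reportable | SADE by definition; excluded by the list of three components | Contradictory |
| Serious, grade 1-2, unrelated to device and procedure | Not reportable | Not a SADE | No required route |

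**Step 3: compare with the stated uses.** Section 12.1 uses 'safety events' as the collective name for all its terms, and its SAE definition carries no relatedness condition. The list promised in 12.10 therefore covers rows 3 and 4 as well. Table B, read literally, also covers them. The 12.3 rationale covers every row, since it mentions AESIs without a grade limit. The reporting list covers rows 1 and 2 only.

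**Step 4: compare rule with rationale.** The paragraph that justifies restricted recording describes a wider scope than the rule that follows it, both on grade and on procedure-relatedness. It cannot serve as the justification for the narrower rule.

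**The case against.** The other side has a substantial case.

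- **A second route exists.** A reader might infer that AESIs are reported only at grade 3 or above, and that serious lower-grade ones never reach LCTC. The protocol does not support that. Serious events at least possibly related to stem, socket or cement go to LCTC at any grade, and Table E classes cases that cannot be assessed as possible. This stands, and it limits the gap to rows 3 and 4.
- **Section 13.4 still works.** A reader might infer that the closure ground needs every serious event and so cannot be applied. It is qualitative, one of several reasons that may be used, and concerns hazard caused by the study treatment. Device-related serious events and grade 3 or above AESIs bear on it directly. It is weakened, not disabled.
- **Other data would pick some events up.** The 6-week visit collects AESIs, antibiotic prescriptions and unplanned contacts (7.5). Unplanned contacts are asked about again at 3-6 months (7.6), and the resource use survey records inpatient stays and emergency attendances (10.4). This stands in part: these are sources from which an event might be noticed, but they do not create a reporting duty, and 12.8.1 keeps the Adverse Events CRF to grade 3 or higher.
- **The restriction is deliberate.** The devices are CE marked with a known safety profile, and the trial is expected to be low risk. Restricting reporting is a legitimate choice. It does not answer the point, because the stated rationale covers more than the rule.
- **The Safety Plan and decision tree may settle it.** Section 12.8 refers sites to the Safety Plan, and neither that plan nor the decision tree's content is available here. Sites may in practice follow 12.3 rather than Table B, so divergence between sites is a possibility, not a finding.
- **Size.** A count of missed events could be produced only by assuming event rates and assuming that none is thought even possibly device-related. The protocol gives no basis for either.

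**Conclusion.** The concern holds in a limited form. A Table C AESI that is serious but grade 1-2, and not considered at least possibly related to stem, socket or cement, has no required route to LCTC. For events unrelated to device and procedure this is a plain gap against the promise in 12.10. For procedure-related events it is a contradiction: 12.6 and the 12.3 rationale bring them in, while the 12.3 reporting list and the 12.6 component list leave them out. As a consequence, the list for the ethics committee and the count available to the TSC may be incomplete.

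The number of events affected cannot be derived from the protocol; with 40 patients, the extra reporting involved should be small. The conclusion rests on reading Table D and section 12.5 as written and on the protocol text alone. It would weaken if the Safety Plan or the decision tree already requires these events to be reported, though the protocol sections would still need to agree. It is worth correcting, but it does not threaten the trial's feasibility conclusions.

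**What to change.** Reconcile Table B and sections 12.3 (rationale and reporting list), 12.6, 12.8.1, 12.8.2 and 12.10 to one reporting scope:

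1. State whether serious events related to the procedure are reportable, as the 12.3 rationale and the 12.6 definition say. Make the 12.3 list and the 12.6 component list agree with that.
2. In 12.3 and 12.8.1, make a Table C AESI reportable on the existing Adverse Events CRF if it is grade 3 or above or meets the 12.5 definition of serious.
3. Reword the Table B row to name the same events.
4. Whatever scope is kept, word 12.10 and 13.4 to refer to the events LCTC will actually hold. If the sponsor prefers to keep the narrower rule, steps 1, 3 and 4 still apply, and the 12.3 rationale must be narrowed to fit.
5. Check the decision tree and the Safety Plan against the result.

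Section 12.7.1 needs no change, since serious adverse events already go into the patient notes. The cost is wording in these sections and, if step 2 is adopted, a few extra pages of an existing form.

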## Reporting requirements decision tree:

**IRAS Ref: 271885** Page 55 of 89

Table C	: Adverse Events of Special Interest (in alphabetical order).
Event	
1.	Cerebrovascular accident
2.	Deep infection
3.	Deep Vein Thrombosis
4.	Dislocation of hip (subluxation or dislocation of joint)
5.	Fracture around joint including femoral shaft perforation or fracture, calcar fracture, trochanteric fracture, acetabular (fracture or perforation) or pelvic fracture (intraoperative)
6.	Fracture around joint including trochanteric avulsion, femoral or acetabular or pelvic fracture (postoperative)
7.	Haematoma
8.	Heterotopic ossification of joint leading to pain or stiffness (periarticular calcification or ossification)
9.	Loosening of implants (early or late, change in position of implants, subsidence of implants or tissue reaction/osteolysis)
10.	Myocardial infarction
11.	Nerve injury (temporary or permanent nerve damage including femoral, obturator, peroneal, sciatic)
12.	Organ/Multiorgan failure
13.	Pain from joint
14.	Pneumonia
15.	Pulmonary Embolism
16.	Revision surgery
17.	Superficial infection
18.	Vascular injury (including iliac, obturator and femoral artery injury)
19.	Wear or fracture or fatigue fracture of implants

**IRAS Ref: 271885** Page 56 of 89

## 12.4 Assessment of Severity

Important Note: A distinction is drawn between **severe** and **serious**. Severity is a measure of intensity, whereas seriousness is defined using the criteria in Section 12.5. However, any AE's with a severity grading of 4 or 5, according to the Clavien Dindo classification system^24 (i.e. life-threatening or fatal), also meet the criteria of serious.

Table D: Clavien Dindo classification system^24.

Grade	Definition
1	
 
Any deviation from the normal postoperative course without the need for pharmacological treatment or surgical, endoscopic and radiological interventions.
 
Allowed therapeutic regimens are: drugs as antiemetics, antipyretics, analgetics, diuretics and electrolytes and physiotherapy.
 
This grade also includes wound infections opened at the bedside.
 

2	
 
Requiring pharmacological treatment with drugs other than such allowed for grade 1 complications.
 
Blood transfusions and total parental nutrition are also included.
 

3a	Requiring surgical, endoscopic or radiological intervention – not under general anaesthesia.
3b	Requiring surgical, endoscopic or radiological intervention – under general anaesthesia.
4a	
 
Life-threatening complication (including CNS complications*) requiring intermediate care or intensive care management – single- organ dysfunction (including dialysis).
 

4b	
 
Life-threatening complication (including CNS complications*) requiring intermediate care or intensive care management – multi- organ dysfunction.
 

5	Death of a patient.
*brain ha	aemorrhage, ischemic stroke, subarachnoidal bleeding, but excluding

#### 12.5 Assessment of Seriousness

**Important Note:** The assessment of seriousness of safety events should be performed by an appropriately delegated, medically qualified member of the site research team.

An AE is termed "serious" if it:

transient ischemic attacks.

- Led to a death, injury or permanent impairment to a body structure or a body function;
- Led to a serious deterioration in health of the subject, that either resulted in:
  - o a life-threatening illness or injury, or

**IRAS Ref: 271885** Page 57 of 89

- o a permanent impairment of a body structure or a body function, or
- in-patient hospitalisation or prolongation of existing hospitalisation (N.B. Planned hospitalisation for pre-existing condition, or a procedure required by the Clinical Investigation Plan, without a serious deterioration in health, is not considered a serious adverse event), or
- Medical or surgical intervention to prevent life threatening illness;
- Led to foetal distress, foetal death or a congenital abnormality or birth defect.

Note: the reporting of pregnancy as an SAE is not required.

## 12.6 Assessment of Relationship to Trial Devices or Procedure

An SAE is termed "related" if it is assessed as being 'related' to the device or procedure if it has a 'possible', 'probable' or 'causal' relationship (highlighted in green within table E below). If assessed as related (to a device or the procedure) it is classified as a Serious Adverse Device Effect (SADE). All SADEs require expedited reporting to LCTC.

The assignment of the relatedness should be made by an investigator with the delegated responsibility of assessing safety events.

Relatedness should only be assigned to the following:

- a. Implant stem
- b. Implant socket
- c. Bone cement

If any doubt about the relatedness exists, the local investigator should inform the LCTC who will notify the Chief Investigator.

In the case of discrepant views on relatedness between the treating investigator and others, the opinion of the treating investigator will never be downgraded and the MHRA/REC will be informed of both points of view.

Table E: Definitions of Relationship

Relationship	Definition	
Not related	Relationship to the device or procedures can be excluded when:	
	
 
the event is not a known side effect of the product category the device belongs to or of similar devices and procedures;
 
the event has no temporal relationship with the use of the investigational device or the procedures;
 
the event does not follow a known response pattern to the medical device (if the response pattern is previously known) and is biologically implausible;
 
the discontinuation of medical device application or the reduction of the level of activation/exposure - when clinically feasible - and reintroduction of its use (or increase of the level of activation/exposure), do not impact on the event;
 
the event involves a body-site or an organ not expected to be affected by the device or procedure;
 
	

**IRAS Ref: 271885** Page 58 of 89

	
 
the event can be attributed to another cause (e.g. an underlying or concurrent illness / clinical condition, an effect of another device, drug, treatment or other risk factors);
 
the event does not depend on a false result given by the investigational device used for diagnosis, when applicable;
 
harms to the subject are not clearly due to use error;
 
In order to establish the non-relatedness, not all the criteria listed above might be met at the same time, depending on the type of device/procedures and the event.
 

Unlikely	Relationship with the use of the device seems not relevant and/or the event can be reasonably explained by another cause, but additional information may be obtained.
Possible	Relationship with the use of the investigational device is weak but cannot be ruled out completely. Alternative causes are also possible (e.g. an underlying or concurrent illness/clinical condition or/and an effect of another device, drug or treatment). Cases where relatedness cannot be assessed or no information has been obtained should also be classified as possible.
Probable	Relationship with the use of the investigational device seems relevant and/or the event cannot reasonably be explained by another cause, but additional information may be obtained.
Causal Relationship	Event is associated with the investigational device or with procedures beyond reasonable doubt when:  • the event is a known side effect of the product category the device belongs to or of similar devices and procedures;  • the event has a temporal relationship with investigational device use/application or procedures;  • the event involves a body-site or organ that  • the investigational device or procedures are applied to;  • the investigational device or procedures have an effect on;  • the event follows a known response pattern to the medical device (if the response pattern is previously known);  • the discontinuation of medical device application (or reduction of the level of activation/exposure) and reintroduction of its use (or increase of the level of activation/exposure), impact on the event (when clinically feasible);  • other possible causes (e.g. an underlying or concurrent illness / clinical condition or/and an effect of another device, drug or treatment) have been adequately ruled out;  • harm to the subject is due to error in use;  • the event depends on a false result given by the investigational device used for diagnosis, when applicable.

**IRAS Ref: 271885** Page 59 of 89

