# 5.2 Patient Participant Transfer and Withdrawal

In consenting to the trial, patient patients are consented to trial treatment, follow-up and data collection. If post-operative voluntary withdrawal occurs, the participant should be asked to allow continuation of scheduled evaluations, and be given appropriate care under medical supervision until the symptoms of any adverse event resolve or the subject's condition becomes stable.

Participants who lose capacity after providing consent and while still in follow-up will be withdrawn from the study. In these instances, data up to the point of withdrawal will still be used for analysis and the patient will not be replaced.

\_

<sup>2 All prostheses and bone cements that are used must be CE marked and used in accordance with their intended use. There is no limitation as to the manufacturer of prostheses used and surgeons will continue to use the implants that they are familiar with. Furthermore, surgeons will be free to use whichever head/socket material and diameter they feel appropriate. The surgical approach, anaesthetic type, rehabilitation after surgery and other concomitant factors will be as per the surgeons' normal care. These factors will be recorded.

**IRAS Ref: 271885** Page 33 of 89

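### Section 12 is inconsistent on whether procedure-related serious events are SADEs, gives USADE the SADE definition, and fixes one manufacturer's leaflets for expectedness, so classification is ambiguous

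*Protocol*

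**What the plan says.** **SADE scope.** Section 12.6 states: "If assessed as related (to a device or the procedure) it is classified as a Serious Adverse Device Effect (SADE"), and requires expedited reporting of every SADE. A few lines later it says "Relatedness should only be assigned to the following" and lists the implant stem, the implant socket and bone cement. The procedure is not on the list. Section 12.3 makes a serious device event reportable to the coordinating centre (LCTC) if it "is assessed as being related a device (i.e. an implant or bone cement"), adds grade 3 or above adverse events of special interest (AESIs), and says nothing else need be reported. Its rationale is wider: recording only AESIs and "Serious Adverse Events that are related to the device or procedure will not affect the safety of participants or the aims of the trial".

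**USADE.** In Section 12.1 the definitions of SADE and USADE are the same sentence: "An ADE which meets the definition of 'serious".

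**Expectedness.** Section 12.11 calls a SADE unexpected if it is absent from the Instructions for Use (IFU). Section 12.12 names four such documents, all from one manufacturer. Footnote 2 to the eligibility criteria in Section 5 says: "There is no limitation as to the manufacturer of prostheses used".

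**Use.** Section 12.10 requires an expedited report to the sponsor and ethics committee of "Any significant difference in quantity of SADEs by implant type that are judged to be clinically important".

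**The concern.** These classes trigger actions. SADE status sets the 5-calendar-day limit for reporting to LCTC (Section 12.8.2) and feeds the comparison by implant type (Section 12.10). USADE status sets reporting to the ethics committee, the sponsor and the MHRA (Sections 12.8.2 and 12.10) and the retention of devices as evidence (Section 12.9). If the text supports two answers for one event, two sites could classify it differently and both be following the protocol. Intra-operative and post-operative safety is a stated objective (Section 2.3), and the feasibility study prepares procedures for a larger trial, so the ambiguity could carry forward.

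**Working it through.** The protocol gives no figure to reproduce, so the check sets the provisions side by side.

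**1. SADE scope: one event under each rule.** Take a pneumonia or deep vein thrombosis (both in Table C) that is treated with drugs, reflects a serious deterioration in health, prolongs the admission, and is attributed to the operation and not to an implant or cement.
- Severity: drug treatment beyond the grade 1 list is Clavien Dindo grade 2 (Table D). The AESI route needs grade 3 or above, so it does not apply.
- Seriousness: a serious deterioration that prolongs hospitalisation is serious (Section 12.5).
- Section 12.6, classification sentence: related to the procedure, so a SADE. Section 12.8.2 then gives 5 calendar days.
- Section 12.6, relatedness list: the procedure cannot be chosen, so no related SADE can be recorded.
- Section 12.3: neither a grade 3 AESI nor device-related, so not reportable.

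Table E does not settle it. Its Not related and Causal rows cover device and procedures, while the Unlikely, Possible and Probable rows mention only the device. The definition of an adverse device effect reaches "the deployment, the implantation, the installation, the operation, or any malfunction of the investigational medical device", but it covers inadequacies in those steps and use error. A complication of having an operation at all falls outside it.

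**2. USADE.** Section 12.1 puts the unanticipated element only under UADE, where the event must not have been identified in the risk analysis report, IFU or protocol. The USADE entry lacks it. Read literally, USADE = SADE, so every SADE would go to the regulator and every device involved would be retained. That is over-reporting, not missed events.

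**3. Expectedness.** The randomised difference between arms is the socket, since both arms use a cemented stem. The reference entries in Section 12.12 are:
- stem, uncemented socket and bone cement: an adverse-event section of the IFU;
- cemented socket: the indications and contraindications section.

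If that section does not list adverse events (its content is not shown), a SADE attributed to a cemented socket would count as unexpected more readily than the same event with an uncemented socket. Separately, a SADE with another maker's device would be tested against a document that may not describe it.

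**4. What each fault can move.** Only the first changes how many SADEs are counted. The second and third change which SADEs are called unanticipated. For scale, 40 patients randomised 1:1 give 40/2 = 20 per arm, so one patient's event moves an arm's proportion by 1/20 = 5 percentage points. This assumes full recruitment, an equal split and no cross-over.

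**The case against.** The strongest reply has four parts.

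- **Other safety routes exist.** Grade 3 or above AESIs reach LCTC whatever their relatedness (Sections 12.3 and 12.8.1). Revision, re-operation for infection, and intra- and post-operative complications are separate secondary outcomes (Section 11.2.2). The steering committee oversees complications generally (Section 18.3). This stands. A reader might infer, because there is no separate data monitoring committee, that SADEs are the only safety signal the steering committee sees. The protocol does not support that, and the report by implant type in Section 12.10 goes to the sponsor and ethics committee.
- **The USADE wording is a slip.** The UADE definition and Section 12.11 supply a working test, applied by the Chief Investigator or a Clinical Coordinator and not by sites. This also stands: the intent is clear, but the definition that governs regulatory reporting is still wrong.
- **Rules limit divergence.** Doubtful relatedness goes to LCTC (Section 12.6), unassessable cases default to Possible (Table E), and all serious events are recorded in the notes (Section 12.7.1). This helps in part. The event traced above is not doubtful: it is clearly procedural and clearly not device-related. The difference between the rationale and the list in Section 12.3 is arguable, since one speaks of recording and the other of reporting. The conflict does not depend on it.
- **Key material is not shown.** The decision-tree figure is missing from the text, Section 12.8 defers to a Safety Plan, and the implants in use at the three sites are not stated. So it cannot be shown that sites would in fact report differently, or that any event would be judged against an unsuitable leaflet. What can be shown is that the protocol permits both.

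**Conclusion.** The three inconsistencies are in the text and should be corrected. The gap in SADE scope is the substantive one. It covers serious, purely procedure-related events that are not grade 3 or above AESIs, and it is the only fault that can alter SADE counts by implant. The USADE definition is a drafting error whose literal effect is over-reporting and unneeded device retention. The reference documents may not describe the implant used, and the two socket types may be judged against different kinds of content.

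The number of events affected cannot be computed, because the protocol gives no event rates. A reader might go further and call the SADE counts unreliable. The protocol supports only that classification is ambiguous and open to inconsistency. Section 11.5 states that no formal safety assessment across arms will be made, and the primary outcome and stop/go rule rest on recruitment, which is unaffected. The conclusion assumes that neither the Safety Plan nor the decision tree overrides the protocol. Even if they resolve the matter in practice, the protocol text still contradicts itself.

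**What to change.** - Decide once whether procedure-related serious events are SADEs. Apply that scope in Sections 12.3, 12.6 and 12.8 and in all rows of Table E, and make the list of items to which relatedness may be assigned match it. The choice is the sponsor's; the passages must agree.
- Define USADE as a UADE that meets the definition of serious. Since UADE also refers to the risk analysis report and protocol while Section 12.11 uses only the IFU, make the two name the same reference.
- In Section 12.12, use the IFU of the implant and cement actually used. It can still be frozen at the first randomisation, as the protocol intends.
- Check the section cited for the cemented socket.
- Align the Safety Plan and decision tree with the result.

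The cost is a wording amendment submitted for ethics approval, a notice to the three sites, and collection of the IFUs for the implants and cements in use there, for the Chief Investigator and Clinical Coordinators. No change to sample size, randomisation or outcome collection is needed.
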